## **Study Timeline**

### *Baseline:*

Participants who meet inclusion and exclusion criteria will be enrolled into the study after consenting to and before receiving treatment. The baseline examination and all baseline questionnaires will be completed within 8 weeks before the index study treatment procedure (facet joint steroid injection or medial branch radiofrequency ablation) as time is needed to obtain insurance authorization for all study procedures in the present study (all procedures in this

study represent usual care procedures: medial branch blocks, facet joint injections, and medial branch radiofrequency ablation).

*Follow-up:*

Routine scheduled follow-up will occur at 1 month (+/- 2 weeks), 3 months (+/- 4 weeks), 6 months (+/- 6 weeks), 12 months (+/- 3 months), and 24 months (+/- 3 months), at which times all follow-up measures will be obtained.

The 3-month follow-up will serve as the time point for the primary outcome analysis of the randomized trial and an intention-to-treat analysis will be used to evaluate for differences in outcomes between the two groups. The 3-month time point provides a reasonable timeframe to evaluate the clinical effects of the lumbar MBN C-RFA while also providing a humane timeframe for crossover to active treatment in those randomized to usual treatment. All subsequent follow-up periods are intended to evaluate long-term clinical outcomes of lumbar MBN C-RFA and will be evaluated with an as-treated analysis.

The study start date and the outcome assessment timeline will begin at the date of the participant's initial facet-targeted treatment. After 3 months, patients who have failed treatment (not meeting criteria for success, as described above) can be offered alternative treatment. Those who cross-over will be considered treatment failures of the original treatment, by definition, and continue on the regular follow-up schedule. A new 2-year follow-up period will begin upon cross-over.

This study is intended to monitor outcomes for 2 years following facet joint intervention. Some patients reporting relief at the 3-month follow-up may experience a return of symptoms afterwards. All patients reporting relief at the 3-month follow-up will be instructed to contact their physician if and when they experience a treatment effect that diminishes by >50%. This can occur at any time following the 3-month follow-up, including the regularly scheduled follow-up intervals. Repeating the facet intervention procedure originally assigned beyond the 3-month follow-up does not reset the follow-up schedule. Patients are also free to choose alternative therapies beyond 3 months. Patients may also develop new low back pain that is different from what is being evaluated, which will be noted.

[figure not shown]

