#### **1.3 Specific Aims:**

1. Determine the proportion of patients with a successful response (defined as 50% or greater improvement in index pain) to lumbar MBN C-RFA versus facet joint injection of corticosteroid at 3 months, and the duration of relief up to 2 years.
2. Evaluate the functional improvement observed in both groups, as assessed by the Oswestry Disability Index (ODI), the PROMIS Physical Function CAT (PF-CAT), and the Patient Global Impression of Change (PGIC); determine the correlation between reduction in pain and improvement in function, as well as the correlation between the

ODI and the PF-CAT in this specific population, to both the anchor score (PGIC) as well as to each other (ODI vs. PF-CAT).

4. Evaluate changes in opioid and non-opioid analgesic use in both groups, as assessed by the conversions to daily morphine equivalent use and Medication Quantification Scale III score.
5. Evaluate differences in the proportion of patients with a successful treatment response in those who reported 100% relief from dual comparative diagnostic lumbar MBN blocks relative to those with at least 80% improvement but less than 100% relief from the dual comparative blocks.
5. Report immediate, short-term, and long-term adverse effects, using a standardized survey that includes a comprehensive query of known adverse events associated with systemic steroid effects.

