### *Follow-up Only:*

- Patient global impression of change (PGIC)
- Adverse effects. Specifically only: spinal infection, epidural hematoma, and neurological damages to the spinal nerve root(s) at the treated level(s).

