## **Study Protocol**

*Treatments Procedures:*

*C-RFA Procedure (Procedure as performed as standard of care clinical practice)*

During the C-RFA procedure, the participant will be positioned prone on a fluoroscopy table. Sterile precautions, including sterile preparation, drapes, and gloves, will be undertaken. A pre-procedure time-out will be performed. Vital signs will be recorded as per usual care for sedation procedures. Patients may be mildly sedated during the procedure, using intravenous midazolam and /or fentanyl. An C-RFA electrode – Coolief® Cooled Radiofrequency Kit (Halyard Health Inc, Alpharetta, GA), will be placed at the junction of the transverse process and the superior articular process in an ipsilateral oblique fluoroscopic view, touching bone, but then with

subsequent withdrawal of the stylet, allowing a 2 mm gap between the electrode tip and the base of the superior articular process given forward projection of the cooled lesion. Appropriate positioning will be confirmed in oblique, anterior-posterior, and lateral fluoroscopic views, as is shown in the below figures per manufacturer guidelines:

Motor testing may be performed at each of the MBNs per physician discretion. Sensory testing is not required, as this technique has been shown to have no influence on treatment outcomes. After appropriate electrode positioning, 1-4 mL of 1-4% lidocaine might need to be used at a given medial branch nerve in order to effectively anesthetize it before lesioning (standard of care range). This is done through an introducer needle for anesthesia during the ablation. The C-RFA lesions will be performed by using the typical C-RFA protocol with lesions performed with the RFA generator (generator is pre-programmed). Once the procedure is completed, all needles will be removed. Following ablation, 0.25-1 mL of 0.25 -0.5% bupivacaine will be injected at each medial branch nerve to provide post procedure analgesia. No corticosteroids will be injected.

For bilateral low back pain, a maximum of 4 facet joints (two on each side) will be denervated by lesioning of up to 6 MBNs. For unilateral low back pain, up to 3 facet joints will be denervated by lesioning up to 4 MBNs.

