2. Global function (Global-10)
3. Analgesic use (MQS III score)
4. Global impression of change (PGIC)
5. Adverse events (Specifically only: spinal infection, epidural hematoma, and neurological damages to the spinal nerve root(s) at the treated level(s))

*Blinding:*

Participants cannot be realistically blinded to their intervention. However, all assessors will be independent and blinded. Participants will remain in their allocated groups throughout the study unless they meet the criteria for crossover treatment. In order to provide an unbiased assessment, the treating physician will be different from the outcome assessor, a trained research assistant.

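### Immediate adverse effects are an aim, but they are first collected at the 1-month visit and no procedure-day source is named

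*Combined protocol and SAP*

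**What the plan says.** The last item of section 1.3, Specific Aims (the second item numbered 5), sets the commitment: "Report immediate, short-term, and long-term adverse effects, using a standardized survey that includes a comprehensive query of known adverse events". The query is to cover the known systemic effects of steroids.

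Outcome Instruments puts adverse effects under Follow-up Only and narrows them: "Adverse effects. Specifically only: spinal infection, epidural hematoma, and neurological damages to the spinal nerve root(s) at the treated level(s". The Secondary Outcomes list repeats that restriction.

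The Study Timeline gives the clock and the visits. On the clock: "The study start date and the outcome assessment timeline will begin at the date of the participant's initial facet-targeted treatment". On the first visit: "Routine scheduled follow-up will occur at 1 month (+/- 2 weeks". Visits at 3, 6, 12 and 24 months follow, "at which times all follow-up measures will be obtained". The same section says that repeating the assigned procedure after 3 months leaves the visit calendar as it was, and that crossover opens a new two-year period.

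On who collects, the Blinding paragraph says that "the treating physician will be different from the outcome assessor, a trained research assistant".

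**The concern.** An immediate effect of an invasive procedure is best recorded when it happens, by someone who is there. As written, the plan's first question about adverse effects comes weeks later, from a person who was not in the procedure room. The treating physician or procedure staff may see the event, but the plan does not say how their observation reaches the study record.

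At stake is one named aim and one secondary outcome. A brief event that has resolved by the first visit, such as a transient nerve-root symptom, may go unrecorded or be poorly dated. A later report of few immediate events could not then be told apart from a failure to ask in time, and events not recorded on the day cannot be reliably recovered afterwards.

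**Working it through.** The plan attaches no figure to adverse-event collection, so there is none to reproduce. The sample size (39 per group, 135 to be enrolled) is not an input. The check is date arithmetic followed by a search for any earlier source.

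**1. Index procedure to first query.** Inputs, from the Study Timeline: day 0 is the first treatment; the first visit is at 1 month, plus or minus 2 weeks (14 days).
- With a 28-day month: 28 − 14 = 14 days; 28 + 14 = 42 days.
- With a calendar month of 365.25/12 = 30.4 days: 30.4 − 14 = 16.4 days; 30.4 + 14 = 44.4 days.

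Either way the gap is roughly 2 to 6 weeks.

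**2. Repeat procedure to next query.** The calendar is not restarted, so the longest wait is the interval between consecutive visits, if the repeat falls just after a visit.

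| Repeat just after | Next visit | Gap at nominal dates |
|---|---|---|
| 3 months | 6 months | 6 − 3 = 3 months |
| 6 months | 12 months | 12 − 6 = 6 months |
| 12 months | 24 months | 24 − 12 = 12 months |

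These are maxima; a repeat later in the interval waits less. The visit windows can stretch them. If the 12-month visit is 3 months early and the 24-month visit 3 months late, the last gap is (24 + 3) − (12 − 3) = 18 months.

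**3. Crossover procedure.** A new two-year period begins. If it uses the same visits, the gap is again that of step 1.

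**4. Search for an earlier source.**
- The C-RFA text mentions vital signs as usual care for sedation. It does not describe recording adverse events for the study.
- The FJI text describes no adverse-event recording.
- The 30-minute recovery period in the Inclusion Criteria belongs to the diagnostic blocks, before study treatment.
- The ancillary treatment log records treatments, not events.
- Data Management mentions standardized case report forms and REDCap, but not what the forms contain or when they are completed.
- No section describes an early telephone call, a chart review for events, or a route from the treating physician to the study data.

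Put side by side, the aim asks for immediate effects and the schedule first asks about them 2 to 6 weeks later.

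**The case against.** The strongest reply is that the operative list holds only three serious kinds of event. A participant is unlikely to forget a spinal infection or an epidural hematoma within six weeks, and such events would probably appear in clinic records. Some of them, infection for instance, would not be expected to show before discharge, so a procedure-day form would have little to record. Much of this stands: while the narrow list applies, the gain is modest. It does not dispose of the point. Nerve-root injury is on the list and may be transient, the aim itself promises a comprehensive query, and the plan names no chart source.

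The plan is also silent rather than prohibitive. A reader might infer that the treating physician is barred from reporting events, or that recall is the only possible source. The Blinding paragraph separates physician and assessor to keep assessment unbiased; it excludes neither physician reports nor records. Nor is the 1-month visit the only collection point: it is the first of five.

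A reader might further infer that the gap favours C-RFA, because the C-RFA text says "Patients may be mildly sedated during the procedure, using intravenous midazolam and /or fentanyl" and the FJI text mentions no sedation. The documents do not support that. Silence in the FJI text does not exclude sedation, no sedation rates are given, and nothing shows that sedation alters later reporting.

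A reader might also suppose that participants lost before the first visit will be counted as event-free. The plan gives no early-loss rate and no such counting rule, and someone who misses only the 1-month visit can still report at 3 months.

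Finally, the figure in the Study Timeline section and the front pages could not be read. A procedure-day entry there cannot be ruled out.

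**Conclusion.** The point holds as a mismatch between a stated aim and a stated collection schedule. The first query comes about 14 to 42 days after the index procedure. After a repeat procedure the wait can reach about 12 months at nominal dates. Transient immediate events may be missed in both arms; how many cannot be estimated from the documents, and no direction of bias between arms is shown. The primary outcome, sample size, power and alpha are untouched.

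This rests on three assumptions: that *immediate*, which the plan does not define, means at or soon after the procedure; that the schedule is followed as written; and that no procedure-day record appears in the parts that could not be read. It is a cheap improvement worth making, not a demonstrated bias.

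**What to change.** Add to Outcome Instruments and the Study Timeline a short procedure-day adverse-event form. The treating physician or procedure staff complete it before discharge for every index, repeat and crossover procedure. Store it in REDCap where the blinded assessor cannot see it. Report immediate events from this form and later events from the scheduled visits, and define *immediate* to match.

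First reconcile the comprehensive query in the Specific Aims with the three-event restriction in Outcome Instruments and Secondary Outcomes, and take the form's event list from the result.

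The cost is one short form per procedure, completed by staff already present, and one database access setting; no extra visit is needed. The form closes the procedure-day gap only. Events that begin after discharge and resolve before the next visit would still depend on the scheduled query.

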#### *FJI Procedure (Procedure as performed as standard of care clinical practice)*

During the C-RFA procedure, the participant will be positioned prone on a fluoroscopy table. Sterile precautions, including sterile preparation, drapes, and gloves, will be undertaken.

Using an oblique fluoroscopic view, the image intensifier will be rotated to optimize the posterior joint space opening. A spinal needle will be advanced under fluoroscopic guidance to enter the posterior joint space. The needle position will be confirmed in both AP and oblique views. Approximately 0.2-1 mL of iodinated contrast medium will be injected to confirm intra-articular placement and no vascular uptake. The injection will be then completed with 0.5 mL of 40mg/mL Kenalog and 0.5 mL of 1-4% preservative-free lidocaine. This technique will be repeated for each facet joint injected.

For bilateral low back pain, a maximum of 4 facet joints (two on each side) will be injected. For unilateral low back pain, up to 3 facet joints will be injected.

*Group Assignments:*

Patients will be randomly assigned to the two treatment groups (C-RFA vs. FJI) at a 1:1 ratio. Participants who reported 50% or more relief of their usual pain (NPRS score compared to baseline) at the 3-month follow-up time point and who subsequently experience a treatment effect that diminishes by > 50% will be offered a repeat procedure. Duration of relief will be considered the time from the provision of the treatment procedure until the participant returns to 50% of their pre-treatment level of pain as reported during scheduled follow-up, or when a repeat treatment procedure is requested and performed.

*Crossover:*

Any time after the 3-month follow-up, any participant who has not obtained adequate pain relief can ask to cross over to alternative treatment group. In doing so, a new 2-year follow-up will begin for this participant who is now placed in the alternative treatment group for the long-term, as-treated outcomes analysis.

*Co-interventions:*

Patients are allowed to receive usual care, including co-interventions, as deemed necessary by the treating physician. Treatments related to the participant's spine condition will be reported on the ancillary treatment log.

*Primary Outcomes:*

The primary outcome for the randomized trial is the proportion of responders, defined by a reduction in NPRS score  $\geq 50\%$  at the 3-month follow-up.

*Secondary Outcomes:*

1. Physical function (ODI and PF CAT)

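### A repeat procedure has no safety contact of its own, so the first adverse-effect query after it can come up to 12 months later on the nominal schedule

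*Combined protocol and SAP*

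**What the plan says.** Under Outcome Instruments, adverse effects are listed among the measures taken at follow-up only, and are limited to three complications: "Specifically only: spinal infection, epidural hematoma, and neurological damages to the spinal nerve root(s) at the treated level(s"). Study Timeline, Follow-up sets the visits at "1 month (+/- 2 weeks), 3 months (+/- 4 weeks), 6 months (+/- 6 weeks), 12 months (+/- 3 months), and 24 months (+/- 3 months"). It is at these visits that every follow-up measure is taken. The same section starts the clock at the participant's first facet-targeted treatment.

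Group Assignments makes repeats part of the protocol. Participants with at least 50% relief at 3 months "who subsequently experience a treatment effect that diminishes by > 50% will be offered a repeat procedure". Study Timeline allows that loss of effect to occur at any time after the 3-month visit, and then says: "Repeating the facet intervention procedure originally assigned beyond the 3-month follow-up does not reset the follow-up schedule".

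For crossover, Study Timeline says "A new 2-year follow-up period will begin upon cross-over". The sentence before it says that these participants stay on the regular schedule.

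The last item of section 1.3 (Specific Aims) commits the study to reporting immediate, short-term and long-term adverse effects by a standardized survey that also covers systemic effects of steroids. Adverse events are the fifth secondary outcome.

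**The concern.** A repeat ablation or injection is the same kind of needle or electrode procedure as the index one, and the listed complications are as relevant to it. Only the index procedure has an explicit 1-month query. The text describes no visit, telephone contact or unscheduled adverse-event report after a repeat. The ancillary treatment log records treatments, not complications, and the one patient-initiated contact described is for loss of effect.

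Three things are at stake:

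- Events after repeats may be recorded late and from long recall.
- An event first reported many months later is harder to date and to attribute to the index or the repeat procedure.
- Repeats depend on how many participants respond and how long relief lasts, and both may differ between arms. A per-participant rate then pools people with one exposure and people with several, with ascertainment that may also differ by arm.

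**Working it through.** The plan gives no figure for the time from a repeat to the next query, so there is none to reproduce. The inputs are the visit months and windows in Study Timeline, and the sample size and response rates in Power Analysis. Four weeks is taken as 1 month, 6 weeks as 1.5 months and 2 weeks as 0.5 month.

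**1. Longest wait.** This is the gap between successive visits, for a repeat done just after the earlier one. The window extremes put the earlier visit as early as allowed and the later visit as late as allowed.

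| Repeat falls between visits | Nominal | Window extremes |
|---|---|---|
| 3 and 6 months | 6 − 3 = 3 months | (6 + 1.5) − (3 − 1) = 5.5 months |
| 6 and 12 months | 12 − 6 = 6 months | (12 + 3) − (6 − 1.5) = 10.5 months |
| 12 and 24 months | 24 − 12 = 12 months | (24 + 3) − (12 − 3) = 18 months |

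At the most favourable windows, the 12-month and 24-month visits are still (24 − 3) − (12 + 3) = 6 months apart.

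**2. No query at all.** This applies to a repeat after the final visit. The window allows that visit from month 24 − 3 = 21, so up to 3 months of the 2-year period can lie beyond it.

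**3. Comparison.** The index procedure is queried at 1 month (± 2 weeks), so at 1.5 months at the latest.

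**4. Illustration.** Assume that repeats are spread evenly over months 3 to 24 (21 months) and that visits are on their nominal dates.

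- Mean wait: (3 × 1.5 + 6 × 3 + 12 × 6) / 21 = 94.5 / 21 = 4.5 months.
- Queried within 1.5 months: (1.5 + 1.5 + 1.5) / 21 = 21%, so about 79% wait longer.
- Waiting more than 6 months: only repeats in months 12 to 18, so 6 / 21 = 29%.

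**5. Pool from which repeats arise.** With 135 enrolled 1:1 and planned response of 80% and 50%: 67.5 × 0.80 + 67.5 × 0.50 = 54 + 33.75 = 87.75, or about 88 responders at 3 months. This is an upper limit. It ignores attrition, and a repeat is offered only to responders who then relapse. The documents give no relapse rate and no uptake rate.

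**6. After the fix.** The longest wait falls to 1.5 months, and the sample size is unchanged.

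**The case against.** Leaving the schedule unreset is right for the main long-term question, since durability has to be measured from the initial treatment. The three listed complications are serious; many would surface in usual care, and a participant could still report them at the next visit. A repeat done shortly before a visit is queried promptly. No confirmatory safety test is planned, and repeats come after month 3. Repeat dates are already needed, because duration of relief ends when a repeat is performed. All of this stands. It does not supply a route for recording an event between visits, or the short-term reporting that the aim promises.

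A reader might infer more than the documents support:

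- **That the 2-year monitoring promise is broken for repeats.** The statement is "This study is intended to monitor outcomes for 2 years following facet joint intervention", but the clock is defined from the initial treatment. No 2 years are promised after each repeat.
- **That crossover procedures certainly get a 1-month query.** This is only an inference from the new follow-up period. The visits after crossover are not listed, and the adjacent sentence points the other way.
- **That some 88 participants will be eligible for a repeat.** That is the projected number of 3-month responders, before relapse.
- **That the safety comparison is biased.** No event rate, recall loss or direction can be derived. Differential ascertainment is a possibility, not a demonstrated bias.

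**Conclusion.** The point holds as a gap in safety data collection. A protocol-offered repeat can go 3, 6 or 12 months without an adverse-effect query on nominal visits, and about 18 months only if the 12-month and 24-month visits fall at opposite ends of their windows. Absence of any query is confined to repeats after the final visit, or to cases where the remaining visit is missed. The mean of 4.5 months and the 79% rest on the even-spread assumption and are illustrative. The number of repeats cannot be derived from the documents.

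The effect is on the completeness and timing of long-term safety data, not on the 3-month primary analysis. One reservation remains: the figure that follows this text in Study Timeline is not shown, and the survey is not reproduced. If either already provides for a contact after a repeat, the text need only say so.

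**What to change.** Keep the efficacy schedule unreset and make four changes.

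1. **Study Timeline, Follow-up.** Add: *The study's adverse-effect survey is collected once at 1 month (± 2 weeks) after every repeat procedure performed during study follow-up, including one done shortly before or after an early final visit.* A scheduled visit that falls within that interval can serve as the contact.
2. **Survey content.** Reconcile the last Specific Aim, which includes systemic steroid effects, with Outcome Instruments and Secondary Outcomes, which name three events only, so that the added contact uses one agreed instrument.
3. **Data Analysis.** Report adverse events per procedure performed, by procedure received and by index, repeat or crossover, beside the per-participant rate.
4. **Crossover.** Reconcile the two adjacent sentences in Study Timeline so that the visits after crossover are explicit.

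The cost is one short telephone or REDCap contact per repeat by the existing research assistant, and one extra table. The denominators come largely from repeat dates that the plan already needs. Participants repeated near month 24 would be followed slightly longer: a repeat at month 24 would be queried by month 24 + 1.5 = 25.5, inside the existing outer limit of month 27 for the final visit.
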